1. BACKGROUND INFORMATION

SHP639 is a 9-amino acid, synthetic, C-type natriuretic peptide (CNP) analog that is a potent and selective agonist of natriuretic peptide receptor B (NPR-B). It is being developed by Shire for the treatment of glaucoma and ocular hypotension (OHT). Interaction of SHP639 with NPR-B would potentially have an intraocular pressure (IOP)-lowering effect with a novel mode of action that targets the primary outflow mechanism that is altered in these diseases.

Natriuretic peptides are potent activators of the cell membrane-bound guanylyl cyclases, thereby increasing the intracellular concentration of cyclic guanosine monophosphate (cGMP). C-type natriuretic peptide or CNP analog activation of NPR-B can consequently increase cGMP leading to various physiological effects (eg, smooth muscle relaxation, vasorelaxation, and vascular remodeling) including trabecular meshwork relaxation. It has been reported in several publications that compounds that increase cellular concentrations of cGMP will lower IOP by potentially increasing aqueous humor outflow through relaxation of the trabecular meshwork (Becker, 1990; Nathanson, 1988; Nathanson, 1992; Stein and Clack, 1994). Targeting the trabecular meshwork pathway, which is the dominant ocular outflow mechanism responsible for the majority of aqueous humor drainage, can potentially translate into an attractive target for treating OHT and glaucoma.

In vitro, SHP639 has shown to be highly selective towards activating NPR-B receptors (50% of maximal effective concentration [EC_{50}]=61.4±11.0nM) when compared with natriuretic peptide receptor A (NPR-A) receptors (EC_{50} =2179±335nM), ie, SHP639 is 35 times more potent for the NPR-B receptor compared with NPR-A receptor.

In vivo, a robust lowering of IOP was noted in rabbits and dogs following topical ocular instillation of SHP639. In rabbit models, a dose-dependent IOP-lowering efficacy (≥40% IOP reduction at 0.6%) was observed and the IOP-lowering effect persisted for at least 8 hours for the highest dose tested (0.6%/180 µg per eye). Single-dose administration also significantly increased outflow facility (trabecular outflow) by 2.6-fold in the same species.

Topical ocular administration of SHP639, at a concentration up to 0.6%, was well tolerated in rabbits and monkeys. The no-observed-adverse-effect level (NOAEL) following 28 days of topical administration was 0.6%, administered as 1 drop, into both eyes, 4 times daily (QID) (total daily dose of 1.51 mg/day of SHP639).

1.1 Indication and Current Treatment Options

Glaucoma is an optic neuropathy characterized by retinal ganglion cell degeneration and death, evident at the optic nerve head, and which results in visual field loss. Glaucoma can be classified by anatomy (open-angle or angle-closure glaucoma) or by etiology (primary, secondary, or congenital). Primary open-angle glaucoma (POAG) can progress asymptotically for months or years, causing a delay in diagnosis and treatment. In contrast, OHT is a condition of elevated IOP without signs of early glaucoma but which increases the risk of developing the disease.

Glaucoma is a leading cause of irreversible vision loss worldwide (Weinreb et al., 2014; Quigley and Broman, 2006). Primary open-angle glaucoma affected approximately 58 million people in 2015; this number is projected to increase to approximately 66 million in 2020 (Kapetanakis et al., 2016). Additionally, approximately 2.71 million Americans had open-angle glaucoma in 2011, a prevalence expected to almost triple to 7.32 million by 2050 (Vajaranant et al., 2012).

Intraocular pressure is the major modifiable risk factor of glaucoma (Leske et al., 2003), including in patients with IOP in the statistically “normal” range (Collaborative Normal-Tension Glaucoma Study Group, 1998). Reduction of IOP has been demonstrated in landmark studies to protect against further damage to the optic nerve in patients with early (Heijl et al., 2002) and advanced (AGIS Investigators, 2000) glaucoma and to decrease the risk of progression to glaucoma in patients with OHT (Kass et al., 2002).

Based on data from the Early Manifest Glaucoma Trial (Heijl et al., 2002) and Collaborative Initial Glaucoma Treatment Study (Lichter et al., 2001), ophthalmologists consider a patient’s clinical status, age, and lifestyle in order to decide on an initial target IOP, along with the therapeutic measures to achieve that IOP. While closely following the patient’s visual fields and optic disc status, the target IOP will be reassessed periodically or if the patient demonstrates evidence of glaucoma progression.

Intraocular pressure elevation can occur because of a decrease in aqueous humor outflow through the trabecular meshwork (conventional pathway) or uveoscleral outflow (unconventional pathway) or a relative increase in aqueous humor production compared to outflow (Goel et al., 2010). Pharmacotherapy options can target any or all of these mechanisms. The main classes of topical ocular hypertensive either decrease aqueous humor production (prostaglandin analogs, α -adrenergic agonists, and cholinergic agonists) or increase aqueous humor outflow (carbonic anhydrase inhibitors, β -blockers, and α -adrenergic agonists). Orally administered carbonic anhydrase inhibitors are more effective at lowering IOP compared with topically applied medication; however, the high incidence of systemic side effects associated with an oral regimen (Weinreb and Khaw, 2004) makes it an unacceptable option for routine clinical use.

1.2 Product Background

1.2.1 Nonclinical Information

In vitro and in vivo primary pharmacology studies, in vitro secondary pharmacology studies to assess “off-target” potential, and in vivo pharmacokinetics and distribution studies were performed. Good Laboratory Practice (GLP)-compliant safety pharmacology studies using SHP639 were conducted in vitro in a human ether-à-go-go-related gene assay and in vivo by the intravenous (IV) route in rats and nonhuman primates (NHPs). Pivotal GLP-compliant 4-week toxicology studies with topical SHP639 were conducted in rabbits and NHPs, with accompanying toxicokinetics. A 4-week toxicology and toxicokinetics study with intravenously administered SHP639 was performed to assess potential systemic toxicity. Rabbits and NHPs are both pharmacologically relevant species and both are commonly used species to assess topical and systemic toxicity in ocular drug development. The topical safety studies in both species included a full assessment of potential systemic toxicity (toxicokinetics, clinical pathology, and anatomic pathology for a full list of organs), such that a single species (NHP) to assess the IV

toxicity of SHP639 was considered appropriate. The SHP639 formulation used in the pivotal topical studies is identical to the proposed clinical formulation. This formulation contains standard components typically used in topical ocular formulations. In vitro and in vivo genotoxicity studies were also GLP compliant.

The nonclinical studies demonstrated that topically administered SHP639 has robust and dose-dependent IOP-lowering efficacy in rabbits and dogs, is distributed to relevant ocular tissues with minimal systemic absorption, and is well tolerated in rabbits and NHPs when administered up to QID for 1 month of treatment at concentrations of up to 0.6% SHP639 (30 μ L drop). Clinical signs of ocular discomfort were minimal, transient, and not associated with any ocular pathology or toxicity. Following topical administration, systemic exposure to SHP639 is very low to nondetectable, suggesting a low risk of producing systemic toxicities. Central nervous system, cardiovascular, respiratory, and renal safety pharmacology and systemic toxicity were characterized following IV SHP639 administration, and SHP639 was well tolerated. The nonclinical findings following IV administration were generally transient and monitorable and/or occurred at systemic exposures markedly higher than those expected clinically. SHP639 was nongenotoxic in in vitro and in vivo assays.

The nonclinical data therefore adequately support the initiation of this clinical study. Refer to the latest version of the SHP639 investigator's brochure (IB) for additional nonclinical information.

1.3 Risk/Benefit and Ethical Assessment

There are no expected benefits to the subjects enrolled in this study. The safety profile of topically administered SHP639 in rabbits and NHPs shows that the compound is well tolerated with no adverse effects up to 0.6% when administered QID as 1 drop (30 μ L) in both eyes.

Although, following IVT administration, corneal opacity was seen clinically, the topical ocular toxicity studies in rabbits and NHPs using an exaggerated dosing regimen of QID for 4 weeks did not demonstrate corneal adverse effects up to 0.6% (in a 30 μ L drop; total daily dose of 1.51 mg).

The topical formulation used for this study is the same as that evaluated nonclinically in rabbits and NHPs, and utilizes a well-characterized and widely used vehicle, similar to the marketed MAXIDEX[®] vehicle. Refer to Section 3.3 of the current SHP639 IB for further details.

Considering topical administration, the safety margin for SHP639 ocular drops is calculated based on approximate conjunctival surface area. As the corneal and conjunctival surface areas in rabbits and humans are similar, the human-equivalent dose to the rabbit NOAEL is equivalent to a drop of 0.6% topical solution when administered QID in both eyes, equivalent to a dose of 1.51 mg SHP639 per eye per day.

As the anticipated toxicities for SHP639 are local ocular discomfort, as noted in the animal studies, the proposed topical concentrations to be administered clinically to both eyes (with the exception of Cohort A single-dose treatment period [SDTP], which will occur in 1 designated study eye only) will initiate as a once daily (QD) administration, and will be escalated to multiple times daily based on clinical tolerability. Frequent, serial ophthalmologic examinations, including thorough slit lamp and retinal examinations, will ensure that any corneal or other effects will be detected early, although it is considered highly unlikely that any such effects may occur. The tables below show the margins for each of the dose and dose schedule escalations proposed, based on 1) SHP639 concentrations/drop numbers, and 2) based on SHP639 μ g/day, using a nonclinical NOAEL (both eyes) of 0.6% QID or 1.51 mg/eye/day.

Margins to proposed clinical concentrations, based on concentration of SHP639 and the number of drops/day, are shown in [Table 6](#).

Table 6 Dose Margins Based on SHP639 Concentration and Dosing Regimen

Topical Concentration	Dose Margin ^a			
	QD/Both Eyes	BID/Both Eyes	TID/Both Eyes	QID/Both Eyes
0.1% (50 µg/drop)	24-fold	12-fold	9-fold	6-fold
0.3% (150 µg/drop)	8-fold	4-fold	3-fold	2-fold
0.6% (300 µg/drop)	4-fold	2-fold	1.5-fold	1-fold

BID=twice daily; NOAEL=no-observed-adverse-effect level; QD=once daily; QID=4 times daily; TID=3 times daily

^a Dose margin is based on concentration and number of drops per day; nonclinical single eye NOAEL/clinical dose.

Rabbit NOAEL for both eyes is 0.6%, 8 drops per day (4 drops per eye).

Margins to proposed clinical doses, based on SHP639 µg/day, are shown in [Table 7](#).

Table 7 Dose Margins Based on SHP639 Daily Dose

Topical Concentration	Dose Margin ^a			
	QD/Both Eyes	BID/Both Eyes	TID/Both Eyes	QID/Both Eyes
0.1% per 50 µL (50 µg/drop)	15-fold	7.5-fold	5-fold	3.75-fold
0.3% per 50 µL (150 µg/drop)	7.5-fold	3.75-fold	2.5-fold	~2-fold
0.6% per 50 µL (300 µg/drop)	2.5-fold	1.3-fold	~1-fold	0.6-fold

BID=twice daily; NOAEL=no-observed-adverse-effect level; QD=once daily; QID=4 times daily; TID=3 times daily

^a Dose margin is based on µg/day dose; nonclinical single eye NOAEL/clinical dose.

The NOAEL is 0.6% = 0.6 mg/100 µL = 0.18 mg/30 µL drop; the actual drop size in the animal studies was 31.5 µL drop (equivalent to 189 µg/drop).

189 µg/drop × both eyes × QID = 1.51 mg (free-base equivalent); the clinical studies propose a maximal volume of 50 µL drop.

Always refer to the latest version of the SHP639 investigator's brochure (IB) for the overall benefit/risk assessment and the most accurate and current information regarding drug metabolism, pharmacokinetics, efficacy, and safety of SHP639

2. STUDY OBJECTIVES AND PURPOSE

2.1 Rationale for the Study

SHP639 is being developed for reduction of IOP in glaucoma patients. It is expected to act through a novel mode of action (NPR-B agonism) that leads to an increase in trabecular meshwork outflow, thus reducing the IOP. SHP639-101 is a first-in-human clinical study for a topical ophthalmic formulation of SHP639. Up to 3 different concentrations (0.1%, 0.3%, and 0.6%) will be explored and safety and tolerability of SHP639 ophthalmic solution will be evaluated. As a secondary objective, the study will also aim to characterize the pharmacodynamics (PD) of SHP639, using IOP as a PD biomarker. The pharmacokinetic (PK)-PD relationship will be explored if the data permit.

2.2 Study Objectives

2.2.1 Primary Objectives

The primary objective of this study is to investigate the safety and tolerability of single and multiple ascending doses of SHP639 ophthalmic solution in subjects with OHT or with POAG.

2.2.2 Secondary Objectives

The secondary objective of this study is to evaluate reduction of IOP, as a PD biomarker, following different SHP639 dosing regimens.

2.2.3 Exploratory Objectives

The exploratory objective for this study is to explore the PK-PD relationship of SHP639 in subjects with OHT or POAG.

3. STUDY DESIGN

3.1 Study Design and Flow Chart

This is a multicenter, randomized, double-masked, placebo-controlled, single- and multiple-dose escalation study. Three different SHP639 concentrations will be studied: 0.1%, 0.3%, and 0.6%. There will be up to 12 cohorts in total, 1 cohort for each dose level and different dosing regimen. Each cohort will consist of 7 subjects for a total of 84 subjects in the study. Eligible subjects will be randomized in a 5:2 ratio to receive either SHP639 or placebo, respectively. The anticipated doses being studied for each dosing regimen are presented in the dose-escalation scheme in [Table 10](#).

A sufficient number of subjects will be screened and enrolled to ensure that at least 6 of 7 subjects complete each treatment in their assigned cohort. In the event that a sufficient number of subjects do not complete a cohort, replacement subjects may be enrolled. Each replacement subject will follow the same screening procedures and randomization sequence as the subject who is discontinued, regardless of when the subject discontinued.

3.1.1 Designated Study Eye

For the purpose of overall analysis, 1 eye will be designated as the primary eye for the duration of the subject's participation in the trial. In Cohort A SDTP, the investigational product will be dosed in the designated study eye only. For all subjects participating in the MDTP, a designated study eye will be also identified and the investigational product will be dosed in both eyes. The following procedure will be used to determine the designated study eye:

- For each subject, the mean baseline IOP at a time point will be the mean of the IOPs on days -2 and -1 at that time point.
- The designated study eye will be the eye with the highest mean baseline IOP at the predose time point.
- If both eyes have equal mean baseline IOPs, the eye with the highest mean IOP at the +2-hour time point will be the designated study eye.
- If both eyes have equal mean IOPs at the +2-hour time point, the eye with the highest mean IOP at the +4-hour time point will be the designated study eye.
- If both eyes have equal mean IOPs at the +4-hour time point, the eye with the highest mean IOP at the +8-hour time point will be the designated study eye.
- If both eyes have equal mean IOPs at the +8-hour time point, the right eye will be the designated study eye.

3.1.2 Screening Period

For all cohorts, the maximum duration of the screening period is 42 days. On the initial visit to the site, the subject will first give informed consent. This will be the date that he/she enters the screening period. After giving consent, the subject will be evaluated against the inclusion and exclusion criteria and undergo the procedures as outlined in [Table 1](#).

During the screening period, subjects will return to the site approximately every 2 weeks for safety evaluations. Subjects requiring a washout from current medications will begin their washout period as required in Section [5.2.2](#) and [Table 8](#).

Following the screening visit, subjects who continue to meet the protocol-specific inclusion and exclusion criteria will return to the site on either Day -3 or Day -2, to reconfirm eligibility criteria for participation and undergo the predose safety and ophthalmologic assessments as outlined in [Table 1](#).

3.1.3 Study Parts

The study will consist of 2 parts, Part 1 and Part 2.

- Part 1 consists of Cohorts A1, A2, and A3, each of which is a single-dose and QD multiple-dose cohort (1 cohort for each of the 3 dose levels), followed by Cohorts B1, B2, and B3, each of which is a twice daily (BID) multiple-dose cohort (1 cohort for each dose level).
- Part 2 consists of Cohorts C1, C2, and C3, each of which is a 3 times daily (TID) multiple-dose cohort (1 cohort for each dose level), followed by Cohorts D1, D2, and D3, each of which is a QID multiple-dose cohort (1 cohort for each dose level).

3.1.4 Cohorts A1-A3

In Cohorts A1, A2, and A3, there will be an SDTP followed by a multiple-dose treatment period (MDTP).

3.1.4.1 Cohorts A1-A3: Single-dose Treatment Period

Subjects will be randomized prior to administration of investigational product on Day 1 after all entry criteria have been confirmed.

One drop of investigational product will be administered topically to a designated eye. The first 3 of 7 subjects will be dosed with a minimum of 1-hour intervals between the subjects for safety purposes. The subject will then undergo assessments at the time points outlined in [Table 1](#) and [Table 2](#).

Subjects will be observed for the next 24 hours with appropriate medical oversight. An ophthalmologist will be on call to assess ophthalmic-related medical issues. If no adverse events (AEs) occur that are consistent with the predefined stopping criteria, the rest of the subjects in the cohort can be administered investigational product in 1 designated eye.

3.1.4.2 Cohorts A1-A3: Multiple-dose Treatment Period

After completion of the assessments scheduled for Day 2 of the SDTP, subjects will enter a washout period. The duration of the washout period will last between 3 and 14 days. A dose escalation meeting will occur prior to the advancement to each cohort (refer to Section 6.2.3.2 for additional details). For each cohort, following a decision to commence the MDTP, subjects will attend the site on Days -2 and -1 to undergo the scheduled safety and ophthalmic assessments. In Cohorts A1, A2, and A3 MDTP, all subjects will be administered investigational product in both eyes. The same dose concentration that was administered during the SDTP of the relevant cohort (A1, A2, or A3) will be administered during the MDTP QD for the next 28 days. Subjects are to place 1 drop in each eye at approximately the same time each day. Refer to Table 1 and Section 6.2.3 for additional details.

Subjects will be admitted to the site on Day 1 and will be discharged after completion of all Day 2 assessments. On Days 7, 14, and 21, subjects will return to the site as described in Table 1. On Day 26, subjects will be readmitted to the site. On Day 27, subjects will continue to self-administer investigational product while undergoing the scheduled assessments. The last dose will be administered on the morning of Day 28. After completion of the assessments scheduled for Day 29, subjects will then be discharged from the site.

Subjects will receive a follow-up telephone call approximately 7 days after being discharged from the site. They will return to the site to undergo antidrug antibody (ADA) sampling approximately 60 days after the last dose of investigational product (Day 88).

3.1.5 Cohorts B1-B3, C1-C3, and D1-D3

Authorization from the sponsor to proceed from 1 cohort to the next is to be received before subjects enter the screening period for Cohorts B, C, and D. Once authorization has been received from the sponsor, subjects are to be admitted to the screening period of the appropriate cohort as previously described in this section.

Subjects will undergo the scheduled safety and ophthalmic assessments on Day -2 and Day -1 (refer to Table 1). Subjects will then be administered investigational product per the sponsor's authorization to proceed to that cohort. In Cohorts B, C, and D, subjects will be administered investigational product in both eyes. Refer to Section 6.2.3 for additional details.

Subjects will continue to self-administer investigational product as instructed for the duration of the MDTP. Subjects will be admitted to the site on Day 1 and will be discharged after completion of all Day 2 assessments. On Days 7, 14, and 21 (± 2 days, each), subjects will return to the site as described in Table 1. On Day 26, subjects will be readmitted to the site. On Day 27, subjects will continue to self-administer investigational product while undergoing the scheduled assessments. The last dose will be administered on the morning of Day 28. After completion of the assessments scheduled for Day 29, subjects will then be discharged from the site.

Subjects will receive a follow-up telephone call approximately 7 days after being discharged from the site. They will return to the site to undergo ADA sampling approximately 60 days after the last dose of investigational product (Day 88).

3.2 Duration and Study Completion Definition

The subjects' maximum duration of participation in the study is expected to be 146 days or approximately 5 months (Cohort A1, A2, and A3). The subjects' maximum duration of participation in the study for Cohorts B, C, and D is expected to be 130 days or approximately 4.5 months.

- Maximum planned duration of screening and Washout 1: 42 days
- Planned duration of treatment period: 2 days for SDTP (Cohort A only) and 29 days for MDTP (all cohorts)
- Planned duration of Washout 2 (Cohort A only): 3-14 days
- Planned duration of follow-up: until Day 88±4 days (final assessment visit and anticipated Study Completion Date for each subject)

The study will be completed in approximately 56 weeks.

The Study Completion Date is defined as the date the final subject, across all sites, completes their final protocol-defined assessment. Please note that this includes the follow-up visit or contact, whichever is later. The Study Completion Date is used to ascertain timing for study results posting and reporting.

3.3 Sites and Regions

SHP639-101 will be a multicenter study conducted in the United States. Approximately 7 sites will participate in the study.

4. STUDY POPULATION

Each subject must participate in the informed consent process and provide written informed consent/assent before any procedures specified in the protocol are performed.

4.1 Inclusion Criteria

The subject will not be considered eligible for the study without meeting all of the criteria below.

Subjects cannot be enrolled or randomized before all inclusion criteria (including test results) are confirmed.

1. Subjects must provide written, signed and dated informed consent to participate in the study in accordance with the International Council for Harmonisation (ICH) Good Clinical Practice (GCP) Guideline E6 and applicable regulations, before completing any study-related procedures.
2. Subjects must be aged from 18 through 90 at the time of consent. This inclusion criterion will only be assessed at the screening visit.
3. Subjects must have OHT or stable early POAG in both eyes with acceptable Humphrey visual fields (HVF). Early POAG for this protocol is defined as healthy appearing anterior chamber angles (Shaffer classification system grade 3 or 4) and focal and/or generalized thinning of the optic disc rim characteristic of glaucomatous disease. An acceptable HVF must have been performed within approximately one year of screening, have a false-positive rate of 25% maximum, false-negative rate of 25% maximum, and fixation loss rate of 33% maximum, and mean deviation of no worse than -6.00 dB.
4. On Day -1, subjects must have a mean IOP of ≥ 24 mmHg at 8:00 AM and a mean IOP of ≥ 22 mmHg at 10:00 AM in at least 1 eye, with an IOP difference of < 4 mmHg between eyes at both of these time points. If only 1 eye meets this criterion, then it will be the designated study eye for pharmacodynamic analysis; this eye will also be used for dosing in Cohort A SDTP (designated study eye criteria are detailed in Section 3.1.1).
5. Subjects must have a best-corrected visual acuity (BCVA) in both eyes of 65 letters on the Early Treatment Diabetic Retinopathy Study chart (Snellen equivalent $\sim 20/60$) or better at the screening and baseline assessments.
6. Subjects must be males or females who are nonpregnant and nonlactating at screening (negative serum beta-human chorionic gonadotropin [β -hCG]); if sexually active during the study, they must agree to comply with the applicable contraceptive requirements (refer to Section 4.4) throughout the study period and for 60 days following the last dose of investigational product.
7. Subjects must have a satisfactory medical assessment with no clinically significant or relevant abnormalities as determined by medical history, physical examination, and clinical and laboratory evaluation (hematology, biochemistry, urinalysis) as assessed by the investigator.

8. Subject must understand and be able, willing, and likely to fully comply with study procedures and restrictions.
9. Subjects must be nonsmokers or have had stable use of tobacco or nicotine-containing products for a 3-month period before signing the informed consent form (ICF).
10. Subjects who drink alcohol must have had stable use of alcohol for a 3-month period before signing the ICF.

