2.4 Identification of Study Eye

For the purpose of overall analysis, 1 eye will be designated as the primary eye for the duration of the subject's participation in the study. In Cohort A single-dose treatment period (SDTP), the investigational product will be dosed in the designated study eye only. For all subjects participating in the multiple-dose treatment period (MDTP), a designated study eye will be also identified and the investigational product will be dosed in both eyes. For Cohort A, the study eye for MDTP will be the same as the study eye in SDTP. For SDTP Cohort A and MDTP Cohorts B, C and D, the following procedure will be used to determine the designated study eye:

- For each subject, the mean baseline IOP at a time point will be the mean of the IOPs on days -2 and -1 at that time point.
- The designated study eye will be the eye with the highest mean baseline IOP at the predose time point.
- If both eyes have equal mean baseline IOPs, the eye with the highest mean IOP at the +2-hour time point will be the designated study eye.
- If both eyes have equal mean IOPs at the +2-hour time point, the eye with the highest mean IOP at the +4-hour time point will be the designated study eye.
- If both eyes have equal mean IOPs at the +4-hour time point, the eye with the highest mean IOP at the +8-hour time point will be the designated study eye.
- If both eyes have equal mean IOPs at the +8-hour time point, the right eye will be the designated study eye.

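### Protocol criterion 4 and the study-eye algorithm in Protocol 3.1.1 and SAP 2.4 can name different eyes, so dosed and undosed eyes could be swapped in the Cohort A single-dose summaries

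*Protocol*

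**What the plan says.** Protocol 4.1, criterion 4 (repeated in the synopsis), works on Day -1 readings alone. At least one eye must have a "mean IOP of ≥ 24 mmHg at 8:00 AM and a mean IOP of ≥ 22 mmHg at 10:00 AM", "with an IOP difference of < 4 mmHg between eyes at both of these time points". It then assigns the eye: "If only 1 eye meets this criterion, then it will be the designated study eye for pharmacodynamic analysis"; and "this eye will also be used for dosing in Cohort A SDTP". It closes with a pointer, "designated study eye criteria are detailed in Section 3.1.1", and does not say which rule prevails.

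Protocol 3.1.1 works on two days: "the mean baseline IOP at a time point will be the mean of the IOPs on days -2 and -1 at that time point". It then says "The designated study eye will be the eye with the highest mean baseline IOP at the predose time point". Ties go to the +2, +4 and +8 hour readings in turn, then to the right eye. It has no clause for a subject with only one qualifying eye.

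SAP 2.4 repeats the 3.1.1 algorithm and states its scope: "For SDTP Cohort A and MDTP Cohorts B, C and D, the following procedure will be used to determine the designated study eye". It also omits the qualifying-eye rule. It fixes the Cohort A study eye in the multiple-dose treatment period (MDTP) as the SDTP one. Both 3.1.1 and SAP 2.4 say that in the SDTP only the designated study eye is dosed; in the MDTP both eyes are.

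**The concern.** Two rules settle the same label from different data. One uses Day -1 at two clock times against thresholds; the other ranks the two-day predose mean. Where one eye alone qualifies, nothing makes it the higher-ranked eye.

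The label matters most in the Cohort A SDTP, because there it separates a dosed eye from an undosed one. Pharmacodynamic parameters are estimated and summarised by study and non-study eye (SAP 12.4, 12.5). SDTP ocular safety summaries are split the same way (SAP 11), including adverse events (SAP 11.1), which the investigator records as left, right or both eyes (Protocol 8.1.4). Suppose a site doses by criterion 4 and a programmer derives the eye from SAP 2.4. For a subject in conflict, the dosed eye's IOP response and ocular events would then be tabulated under the non-study eye.

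**Working it through.** The plan gives no figure to reproduce. The check is whether one eligible subject can be given two study eyes.

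**Inputs.** Day -1 thresholds of 24 mmHg at 8:00 and 22 mmHg at 10:00, and a between-eye difference below 4 mmHg at both times (criterion 4). IOP above 32 mmHg in either eye excludes (Protocol 4.2, criterion 4). Ranking uses the mean of Day -2 and Day -1 at predose (3.1.1, SAP 2.4). I take predose as 8:00 and +2 hours as 10:00.

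**Two constructed subjects** (mmHg, 8:00/10:00):

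| | Right, Day -2 | Right, Day -1 | Left, Day -2 | Left, Day -1 |
|---|---|---|---|---|
| Subject 1 | 24/22 | 24/22 | 26/21 | 26/21 |
| Subject 2 | 24/22 | 24/22 | 27/23 | 23/22 |

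*Subject 1.*
- Right eye on Day -1: 24 ≥ 24 and 22 ≥ 22, so it qualifies.
- Left eye on Day -1: 26 ≥ 24 but 21 < 22, so it fails.
- Differences are 26 − 24 = 2 and 22 − 21 = 1, both below 4. No reading exceeds 32. The subject is eligible.
- Criterion 4 gives the right eye.
- Mean predose: right (24 + 24)/2 = 24; left (26 + 26)/2 = 26. Protocol 3.1.1 and SAP 2.4 give the left eye.

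*Subject 2.*
- Left eye on Day -1: 23 < 24, so it fails. The right eye qualifies.
- Day -1 differences are 1 and 0. The subject is eligible.
- Criterion 4 gives the right eye.
- Mean predose: right 24; left (27 + 23)/2 = 25. Protocol 3.1.1 and SAP 2.4 give the left eye.

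The rules therefore conflict in two ways: through the 10:00 threshold, which the ranking ignores, and through Day -2, which criterion 4 ignores. Neither example reaches a tie-break or needs any assumption about variability.

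**Frequency, illustrative only.** The documents give no IOP variances. I simulated both eyes on both days at both times and applied the limits above. Every input was assumed: mean 8:00 IOP 24 to 26, 10:00 mean 1.5 lower, between-subject SD 2.5, between-eye SD 0.7 to 2, and SD of a time-point value 0.5 to 2 (mmHg).
- The rules disagreed in 0.3% to 10.5% of eligible subjects.
- The rate is driven mainly by the time-point SD. With mean 25 and between-eye SD 1.0, it was 0.6%, 2.6%, 5.3% and 8.1% at SDs of 0.5, 1.0, 1.5 and 2.0.
- Cohort A plans 3 × 7 = 21 subjects, so the expected number of conflicts runs from 21 × 0.003 ≈ 0.06 to 21 × 0.105 ≈ 2.2.

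**The case against.** The strongest answer is that the text can be read as coherent. Criterion 4 is a specific, conditional rule that points to 3.1.1 for the general procedure. So the sole qualifying eye comes first and the algorithm covers everyone else. That is a reasonable reading, but neither 3.1.1 nor SAP 2.4 states it. A programmer who follows SAP 2.4 as written would not apply it.

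A second answer is that the SAP already ties the SDTP study eye to the dosed eye. SAP 2.4 says only the designated eye is dosed, and SAP 11.6.1 limits SDTP drop comfort to the study eye. The site must designate an eye before dosing, and nothing says the analysis will re-derive it and override the site. This carries weight. A reader might infer that SDTP pharmacodynamics will be read from undosed eyes, and the documents do not support that. A swap needs a site dosing by criterion 4, an analysis deriving by SAP 2.4, and no comparison of the two. But SAP 2.4 also sets the algorithm as the procedure for exactly this period. If the dosed eye is the study eye by definition, the conflict only moves to which eye the site was told to dose.

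Third, both eyes are reported for IOP (SAP 11.6.2.9) and for pharmacodynamic parameters, and listings are by eye. So nothing is lost and a swap could be traced. That stands. So does the point that IOP is a secondary, descriptive endpoint, and that the SDTP IOP tables are not marked for the interim analysis in SAP 16.

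**Conclusion.** The conflict is real and follows from the text alone: the two rules can assign different eyes to an eligible subject, and no precedence is stated. The gap is in Protocol 3.1.1 as well as SAP 2.4. The consequence is conditional and limited to mislabelling in the Cohort A SDTP study-eye and non-study-eye summaries, with the label carried into the Cohort A MDTP.

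The frequency cannot be derived from the documents. The range from under 1% to about 10% of eligible subjects rests wholly on assumed variances, and it counts conflicts between rules, not analysis errors. A reader might go on to infer a stated chance of a contaminated cohort. With 5 active subjects per cohort, one swapped active subject would remove at most 1/5 = 20% of that cohort's mean study-eye effect, if the undosed eye does not respond. That is a ceiling for a cohort in which a swap has already occurred, not an expected loss.

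A reader might also see a comparable problem in the MDTP. Both eyes are dosed there and must lie within 4 mmHg of each other at both entry times, so the effect is minor.

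**What to change.** - The sponsor should reconcile Protocol 4.1 criterion 4 (and its synopsis copy), Protocol 3.1.1 and SAP 2.4 so that all give the same study eye for every eligible subject. Criterion 4 also decides which eye is dosed, so I give no view on which rule should prevail.
- SAP 2.4 should state that for the Cohort A SDTP the analysis study eye is the eye actually dosed. It should add a check of the derived eye against the dosed eye, with disagreements listed.
- First confirm that the dosed eye is recorded in the eCRF or source. The in-clinic dosing details listed in Protocol 6.5 are time, date, dose level and regimen; the eye is not among them.

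The cost is a wording change and one data check. If the dosed eye is on record, no new data are needed. No sample-size figure changes.
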